#### **OPERATIVE DAY PRE-SURGERY**

- Confirm allocated drinks consumed as per instructions & document
- · Thirst and hunger sensation VAS score
- Blood samples on morning of surgery fasted (before consuming the intervention) if not done in POAC.
  - Fasting Glucose
  - Fasting Insulin (3 sample to be taken at 5 minute intervals)
  - Cortisol
  - o CRP
  - HbA1c (if not recently measured)
- Duration surgery (obtained from Theatreman system)
- Volume of blood loss
- Description of operation and type of primary analgesia obtained from Theatreman system or ERP Database
- Calories consumed

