## METHODS FOR ANY ADDITIONAL ANALYSES (EG, SUBGROUP AND ADJUSTED ANALYSES)

If differences are observed in baseline demographic and/or clinical variables prognostic of outcome, then the analysis of the primary and secondary outcomes will be adjusted for using regression-based analysis appropriate to the type of outcome variable. The trial statistician will describe details of sub-group analysis in the statistical analysis plan if possible.

DEFINITION OF ANALYSIS POPULATION RELATING TO PROTOCOL NON-ADHERENCE (E.G., AS RANDOMISED ANALYSIS), AND ANY STATISTICAL METHODS TO HANDLE MISSING DATA (EG, MULTIPLE IMPUTATION) All analysis will be performed according to the intention to treat principle. The primary analysis will be based only on data obtained; sensitivity analysis will explore sensitivity to assumptions around missing data and details will be included in the statistical analysis plan devised by the trial statistician.

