#### WITHDRAWAL OF A PATIENT

In consenting to the trial, patients are consenting to the trial intervention they are allocated, assessments, and data collection. However, patients can withdraw from the SuperStarch Study at any time during the trial. If a patient explicitly states that they no longer wish to take part or contribute further data to the trial, their decision must be respected. The patient's withdrawal from the trial should be recorded in the patient's medical notes and no further data collected. All data collected up to the point of withdrawal will be included in the trial analysis. However, if a patient withdraws consent for any of their data to be used, these will be confidentially destroyed immediately. If a patient is randomised and later found to be ineligible, or the responsible clinician feels that it is no longer appropriate for the patient to continue taking part, then they will be withdrawn from the study and the reason for withdrawal indicated in the medical notes. Patients withdrawn will not be replaced.

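### Patients withdrawn after randomisation for ineligibility or by the clinician have no provision for continued outcome collection, so withdrawals before POD 1 fall out of the intention-to-treat comparison

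*Protocol*

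**What the plan says.** Protocol section 9.3, under the heading on withdrawal of a patient, covers three routes out of the study.

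- **The patient's own decision.** The withdrawal "should be recorded in the patient's medical notes and no further data collected".
- **Late ineligibility.** The rule opens "If a patient is randomised and later found to be ineligible".
- **The responsible clinician's judgement.** If the clinician feels it is "no longer appropriate for the patient to continue taking part, then they will be withdrawn from the study".

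The same paragraph adds "All data collected up to the point of withdrawal will be included in the trial analysis" and "Patients withdrawn will not be replaced". For the second and third routes it does not say whether outcome data are still collected.

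Section 7.3 states "All analysis will be performed according to the intention to treat principle", then "The primary analysis will be based only on data obtained", and leaves sensitivity analyses for missing data to the SAP.

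The primary outcome (section 5.4) is the change in HOMA insulin resistance from baseline to POD 1. Consent, randomisation and dispensing take place at the preoperative assessment clinic (sections 5.3 and 9.3). Only patients are blinded (section 6.2), and the research team knows the allocation (section 5.3).

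**The concern.** Intention to treat needs outcomes from the patients who were randomised, whatever happens to them afterwards. The withdrawal rule takes some of them out of the study for reasons other than their own wish and provides no follow-up. For anyone withdrawn before POD 1, keeping the data collected so far does not help the primary analysis, because the outcome does not yet exist. A SAP can decide how to handle missing values, but it cannot recover blood that was never drawn.

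Two things are at stake. The first is precision in a trial of 40 patients. The second is the comparability of the arms, if a discretionary decision to withdraw is taken by someone who may know the allocation. Section 6.2 defends single blinding on the ground that the endpoint is objective. That protects the measurement, but not the choice of who is measured.

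**Working it through.** **1. Can ineligibility come to light after randomisation?** Setting the sections side by side:

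- Section 5.2 excludes patients with fasting glucose above 5.5 mmol/l and/or HbA1c above 5.7%.
- Section 7.1 (preoperative assessment clinic) lets point-of-care glucose, or an earlier HbA1c result if there is one, confirm eligibility.
- Section 7.1 lists HbA1c among the clinic samples and again among the operative-day samples: "HbA1c (if not recently measured"). The appendix on blood sampling shows that it is a laboratory assay.
- Randomisation is at the clinic.

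So a patient with no recent HbA1c can pass on glucose, be randomised and take the powder home, and then have an HbA1c above 5.7%. The documents give no figure for how often this would happen.

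**2. What happens to the primary outcome?** Withdrawn before the POD 1 sample, with no further sampling: no outcome, and absent from an observed-data analysis. Withdrawn after the POD 1 sample: kept in the primary analysis, with only later outcomes lost.

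**3. Reproduce the planned sample size** (section 5.6: difference 15, SD 16, two-sided 0.05, power 80%, 10% attrition).

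n per arm = 2 × (1.960 + 0.842)² × (16/15)² = 2 × 7.85 × 1.138 = 17.9, so 18. Then 18/0.90 = 20.

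This matches the stated 20 per group, so the point does not rest on a sample size error. The exact t-test needs 18.87, so 19 per arm, or 22 after attrition, which is close to the plan.

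**4. Cost in power** (standardised difference 15/16 = 0.9375):

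| Analysed per arm | Lost of 40 | Power, t-test | Power, normal approximation |
|---|---|---|---|
| 20 | 0 | 82.4% | 84.3% |
| 18 | 4 (10%) | 78.0% | 80.3% |
| 16 | 8 (20%) | 72.8% | 75.5% |

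The 18-per-arm row is the attrition already planned for. Withdrawals under section 9.3 draw on the same allowance of two patients per arm as every other loss.

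**5. Bound on bias.** This is an illustration under assumptions that are not in the documents: no true difference, normal data with SD 16, 20 per arm, 200,000 simulations, and the highest values removed from one arm only.

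| Removed from one arm | Bias (points) | Share of the 15-point target | Type I error |
|---|---|---|---|
| 1 | 1.6 | 1.6/15 = 11% | 6.8% |
| 2 | 2.9 | 2.9/15 = 19% | 10.1% |
| 3 | 4.2 | 4.2/15 = 28% | 14.4% |

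This is a worst case, not a forecast. Removal unrelated to arm and outcome gives no expected bias and costs only power.

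**The case against.** The strongest reply is that the protocol contains no contradiction. A reader might infer that section 9.3 excludes these patients from analysis and so conflicts with intention to treat. It does not say that: withdrawal from the study is not exclusion from analysis, and data up to withdrawal are expressly kept. The instruction to collect nothing further is written for patients who decide to leave, and for the other two routes the text is silent. This stands. What remains is that the rule uses the same word for all three routes and provides for no continued sampling, so staff could reasonably stop.

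A reader might also infer that the patients removed would be those with the most extreme outcomes. For HbA1c the documents do not support this. The operative-day sample is taken before the drink, so the result cannot depend on the drink. The outcome is a change from baseline, and section 4.1 attributes postoperative resistance to surgical trauma rather than to predisposing factors. The late HbA1c route is also narrow, because it applies only to patients who have already passed on glucose.

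A third inference would be that conversion to open surgery triggers withdrawal. No section says so.

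Lastly, that the responsible clinician knows the allocation is inferred from patient-only blinding. It is not stated, although nothing prevents it.

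**Conclusion.** The point holds as a defect in the withdrawal rule. Randomised patients found ineligible or withdrawn by the clinician leave the study without replacement and without provision for outcome collection. Those who leave before POD 1 are lost from a primary analysis that is described as intention to treat. The protocol itself creates the occasion for this by allowing HbA1c to be drawn after randomisation.

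The size depends on a withdrawal rate that the documents do not give. For losses on HbA1c the cost is mainly precision: power falls from 82.4% with everyone analysed to 78.0% at 18 per arm and 72.8% at 16, on the protocol's own difference and SD. For discretionary withdrawal there is a risk of bias of unknown size. The simulated 2.9 points for two patients needs every removal to fall in one arm and to take its highest values. Nothing in the documents shows that selective removal would occur.

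**What to change.** Amend the withdrawal paragraph of section 9.3 to separate stopping participation or the drink from stopping outcome collection. Unless the patient withdraws consent to data collection, a randomised patient who is found ineligible or is withdrawn by the clinician should:

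- be recorded as a protocol deviation, with the reason;
- still have the POD 1 to 3 samples and the other outcomes collected;
- be analysed in the allocated arm, with exclusion of such patients only as a sensitivity analysis.

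What a late HbA1c result or a clinician's judgement means for the patient's care stays with the investigators, and the amendment need not address it.

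The cost is one paragraph in a protocol amendment, with no additional patients or visits and no change to the planned 40. Consent as section 9.3 describes it already covers assessments and data collection. The downside is that a few ineligible patients remain in the primary analysis. The change should be in place before any patient is affected, because missed samples cannot be recovered.

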#### 9.4 CONFIDENTIALITY

Identifiable patient data, including full name, full postal address, date of birth and NHS number will be required by the CI and research team to maintain a screening and enrolment log and ensure follow up for detection of AE. This information will be kept together with all copies of consent forms in the Master Site File securely in the R&D Department. The trial team will not disclose or reproduce any information by which patients could be identified. Data will be entered and stored securely on a ELHT drive folder, with only the research team having access, within the SuperStarch Study excel spreadsheet, which will be password protected by the research team.

## 9.5 Declaration of interests

The CI has no financial or competing interest to disclose regarding this study.

## 9.6 Access to data

Only the CI, co-investigator, the Clinical Research Fellows and the Trial Statistician will have access to the final trial dataset, which will be anonymised.

#### 9.8 DISSEMINATION POLICY

We anticipate the results of this study to be published by peer-reviewed journals and presented at international surgical, anaesthetic and perioperative medicine conferences.

Ongoing progress of the trial will be disseminated locally within the hospital trust via newsletters, emails and updates at divisional and department meetings as well as ERP Operational Meetings. All patient data will be anonymised before publication.

## 10. Appendices

#### 10.1 ERP

#### PRE-OPERATIVE:

- Pre-operative assessment, planning and preparation with CPET assessment if  $\geq$ 60 years or <60 years with cardiorespiratory co-morbidity.
- Provide ERP pack: information leaflet, patient diary and allocated pre-operative carbohydrate intervention to be consumed as detailed in the intervention section.
- Bowel preparation: Upper GI resection and right sided colonic resections none; Left sided colonic resections, rectal resections and radical cystectomies phosphate enemas on the morning of surgery.
- Paracetamol 1gm and Gabapentin 300mg orally.

#### INTRA-OPERATIVE:

- GA and regional analgesia techniques preferred.
- Multimodal anti-emesis
- Nasogastric tube insertion avoided.
- Surgical drains minimised.
- Goal directed fluid therapy.
- Hotline® iv fluid warmers and Bair Hugger™ external warming blanket with temperature monitoring to maintain normothermia.

#### POST-OPERATIVE:

- Maintenance of regional analgesia.
- Multimodal oral analgesia: paracetamol 6 hourly PO or IV if not tolerating oral; Ibuprofen 400mg 8hrly PO once tolerating full oral diet and gabapentin 100mg 8hrly PO.
- Buccastem 3mg 8hrly buccal for 48 hrs.
- 4 x 60m walks per day from Day 1 postoperatively.
- Minimise/avoid iv fluid and promote 2 litres/day oral fluid.
- Removal of urinary catheters on day one unless an epidural in situ in which case at discontinuation of epidural.
- Encourage full oral diet from day 1 postoperatively.

#### 10.2 SURGICAL FITNESS DISCHARGE CRITERIA:

- ability to pass flatus,
- open bowels,
- tolerate oral diet,
- pain control adequate with oral analgesia
- and the patient willing to go home.

## 10.2 BLOOD SAMPLING & HOMA CALCULATION OF INSULIN RESISTANCE

#### **BLOOD SAMPLING**

The HbA1C will be collected in an EDTA sample (both centres will analyse these samples using TOSOH HPLC analysers), 1.5mls blood for cortisol in a serum gel tube (both centres will analyse these samples with Advia Centaur analysers), insulin with 5-10ml of blood in a lithium heparin (orange) tube. The insulin samples need to be received in laboratory within 30 minutes, then centrifuged and frozen for transport to Central Manchester Foundation Trust laboratory in the case of Royal Blackburn Hospital. The Royal Surrey County Hospital will perform this test in-house. Both sites use Mercoda insulin ELISA kit. Serum Glucose samples will be collected in a yellow topped tube. Royal Blackburn Hospital uses an Ortho Vitros analyser and the Royal Surrey County Hospital uses Siemens Advia. However external proficiency testing data shows that on average the methods perform within 2.5% of each other, which is acceptable.

## CALCULATION OF INSULIN RESISTANCE

Insulin resistance will be calculated using the University of Oxford Diabetes Trial Unit HOMA calculator (freely available from https://www.dtu.ox.ac.uk/homacalculator/index.php). Although the Clamp method is considered the "gold standard" for assessing insulin sensitivity this is limited to small-scale intensive physiological investigations and not pragmatic for anything larger i.e. our proposed study.

The homeostatic model assessment (HOMA 1) of pancreatic  $\beta$ -cell function was first described by Matthews et al in 1985. This technique uses basal glucose and insulin or C-peptide concentrations to calculate  $\beta$ -cell function and insulin sensitivity. Insulin resistance is calculated as the inverse of sensitivity (%IR = 100/%IS).

The University of Oxford calculator is based upon the updated HOMA 2 computer model. This model is accurate across a range of insulin (1-2200pmol/l) and glucose (1-25mmol/l). This non-linear model is optimised to calculate insulin sensitivity from fasting glucose and insulin levels. This method is shown to correlate well with the 'gold standard' euglycaemic ( $R_s = 0.85$  to 0.88, p < 0.0001) and hyperglycaemic ( $R_s = 0.61$ , p < 0.01)

[figure not shown]
clamp methods of calculating insulin sensitivity and has been used as a measure of insulin resistance in over 500 publications to date.

The Clamp techniques reflect the stimulated state and the HOMA technique reflects the basal state. The Clamp allows differentiation between liver EGP and peripheral tissue (primarily skeletal muscle) glucose uptake regarding insulin sensitivity whereas HOMA does not differentiate between the sources of insulin resistance.

Fortunately this will not be an issue in our study as it has been shown by Soop et al that postoperative insulin resistance shifts from exclusively peripheral tissue insulin resistance, with a very minor role from the splanchnic tissues, in the first 24 hours, to a substantial role from liver EGP at the third postoperative day onwards. Therefore any insulin resistance measured in our study will be assumed to align with the respective tissues depending on the postoperative timing.

Insulin secretion is pulsatile so three separate blood samples will be taken for insulin at five-minute intervals at each time point and the mean value along with a measure of dispersion. This improves the coefficient of variation from 10% for one sample to 5.8% for three samples.

The samples will be very carefully handled as haemolysis degrades insulin.

HOMA2 MODEL FROM: WALLACE, T. M., LEVY, J. C., & MATTHEWS, D. R. (2004). USE AND ABUSE OF HOMA MODELING

# 10.3 POSTOPERATIVE QUALITY OF RECOVERY SCALE (PQRS)

(http://www.pqrsonline.org)

Physiological Factors
Blood Pressure
Heart rate
Temperature
Respiration
Oxygen use to maintain Sp02
Airway
Agitation
Consciousness
Responsiveness
Noiciceptive Factors
Pain
Nausea and vomiting

Emotional Factors
Depression
Anxiety
Cognitive Factors
Orientation
Memory

## 10.4 ASA Score (ASA Physical Status Classification System)

ASA Physical Status 1: A normal healthy patient

ASA Physical Status 2: A patient with mild systemic disease

ASA Physical Status 3: A patient with severe systemic disease

ASA Physical Status 4: A patient with severe systemic disease that is a constant threat to life

ASA Physical Status 5: A moribund patient who is not expected to survive without the operation

ASA Physical Status 6: A declared brain-dead patient whose organs are being removed for donor purposes

## 10.5 POSSUM Score

see http://www.riskprediction.org.uk

## 10.6 POSTOPERATIVE MORBIDITY SURVEY (POMS) SCORE

Morbidity type	Criteria				
Pulmonary	De novo requirement for supplemental oxygen or other respiratory support				
	(e.g. mechanical ventilation or CPAP)				
Infectious	Currently on antibiotics or temperature >38°C in the last 24h				
Renal	Presence of oliguria (<500mls/day), increased serum creatinine (>30% from				
	preoperatively), or urinary catheter in place for non-surgical reason				
Gastrointestinal	Unable to tolerate an enteral diet (either by mouth or via a feeding tube) for				
	any reason, including nausea, vomiting and abdominal distension				
Cardiovascular	Diagnostic tests or therapy within the last 24h for any of the following: de				
	novo myocardial infarction or ischaemia, hypotension (requiring				
	pharmacological therapy or fluid therapy >200ml/h), atrial or ventricular				
	arrhythmias, or cardiogenic pulmonary oedema				
Neurological	Presence of a de novo deficit, coma, or confusion/delirium				
Wound complication	Wound dehiscence requiring surgical exploration or drainage of pus from the				
	operation wound, with or without isolation of organisms				
Haematological	Requirement for any of the following within the last 24h; packed erythrocytes,				
	platelets, fresh frozen plasma or cryoprecipitate				
Pain	Surgical wound pain significant enough to require parenteral opioids or				
	regional analgesia				

## 10.7 REFERENCE RANGES FOR DIAGNOSING PRE-DIABETES AND DIABETES

# Blood Test Levels for Diagnosis of Diabetes and Prediabetes

		A1C (percent)	Fasting Plasma Glucose (mg/dL)	Oral Glucose Tolerance Test (mg/dL)	
	Diabetes	6.5 or above	126 or above	200 or above	
	Prediabetes	5.7 to 6.4	100 to 125	140 to 199	
	Normal	About 5	99 or below	139 or below	

Definitions: mg = milligram, dL = deciliter

For all three tests, within the prediabetes range, the higher the test result, the greater the risk of diabetes.

## 10.8 ULTRASOUND MEASUREMENT GASTRIC VOLUME

In the anaesthetic room the head of the anaesthetic trolley will be elevated to 45° and the cross sectional area (CSA) of the gastric antrum will be measured at the level where the abdominal aorta and left lobe of the liver are visible using real-time ultra-sonography (Sonosite MicromaxxTM, Sonosite TitanTM or Sonosite S-Nerve portable ultrasound machine with a 3.5 MHz linear transducer) followed by the same measurements in a right lateral decubitus (RLD) position. See Fig 1. for technique. Measurements need to be taken with the antrum at rest, between peristaltic contractions. The CSA must be measured from serosa to serosa, including the full thickness of the gastric wall.

The following equation is used to calculate Gastric Volume (GV): GV (ml)=27.0+14.6×right-lat CSA −1.28×age (for RLD position)

GV (ml)= $-215+57 \log CSA (mm^2) - 0.78 age (yr) - 0.16 height (cm) - 0.25 weight (kg) (for semi-sitting position)$ 

Gastric antral ultra-songraphy measurement has shown adequate sensitivity to measure volumes of 25mls.

The cutoff value of antral CSA of 340 mm^2 for the diagnosis of risk gastric reflux is associated with a sensitivity of 91%, a negative predictive value of 94%, an acceptable specificity of 71%, and a positive predictive value of 63%. Measurements of gastric emptying rate are highly reproducible, with an inter-observer systematic measurement error of 0.3% and a random measurement error of 10.9% between different observers, with intra-observer variability similar to inter-observer variability. A minimum of 200 ml of gastric fluid volume is considered necessary to induce passive regurgitation and pulmonary aspiration.

[figure not shown]

Fig. 1. (A) Transducer position to scan the gastric antrum. (B) Example of a gastric ultrasonographic image. (C) Example of measurement of the antral area.

[figure not shown]

Fig 5 Two alternate methods to measure antral CSA. (A) illustrates a method based on two perpendicular diameters (cranio-caudal and anteroposterior). (B) illustrates a free-tracing method following the outer border of the antrum at the level of the gastric serosa.

